### **8.4 Effectiveness Outcomes.** We will collect data on an array of knowledge, behavioral, and clinical outcomes.

Medication Adherence. Adherence will be measured using: 1) the Ask-12 Scale that assesses general medication attitudes and beliefs, 2) patient self-report of how many pills and how often each medicine was taken over the last 24 hours; 3) in-person and/or phone pill count using established guidelines employed by our team [R01HS00167; PI [name]]; 4) a biologic measure using tacrolimus levels. For 24 hour recall, correct dosing will be measured as yes/no per drug, having properly shown dose (# pills), spacing (hours between doses), frequency (times per day), and total pills/day. For pill count, we will assess adherence within drug calls. If a patient fills a prescription for a drug in a class and then switches to another drug within the same class, all prescriptions will be summed in the numerator. Adherence will be treated both continuously and dichotomously (adherent  $\geq 80\%$ ).

Biologic Measure. Medication adherence to IS medications will also be assessed by computing the standard deviation (SD) of a series of tacrolimus levels obtained for routine monitoring using validated methods. Standard clinical practice at participating centers includes routine monitoring of tacrolimus levels. Tacrolimus levels obtained during acute illness will not be included in the SD calculation. This schedule should result in >30 levels in the first 6 months post KT, 12 levels in months 6-12, 6 levels in months 13-18, 6 levels in months 19-24; and 6-8 levels per year after the second year. Laboratory methods for measurement of whole blood levels are standardized, which should reduce variability between sites. SD calculations will be made using  $\geq 4$  levels obtained over 6 months based on availability. A higher SD indicates more variability between individual measures, and is highly correlated with less stable medication intake (non-adherence) and graft rejection. A SD of the mean levels of  $\geq 2.5$  will be indicative of non-adherence. This biologic measure of adherence will be calculated at 6 month intervals to correspond to interviews.

Composite adherence measure. Each individual measure of adherence has advantages and limitations, thus we will use multiple measures as recommended by experts. Maximum

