likelihood estimation will be used to create a composite adherence metric by generating a single factor score from the 5 measures of adherence.

**Regimen Knowledge:** Patient identification of drug names and indication will be assessed via assessments used previously by [name] and colleagues (ref). Patients will be asked about each of these via structured, open-ended items. Understanding of proper dosing will be assessed using the 24 hour recall task described above, but patients will be given credit if they demonstrate knowledge of how to take their medication correctly regardless of their actual behavior. From this assessment, we can also determine how patients are taking their entire multi-drug regimen, and if medications are consolidated in the most efficient manner. We will examine the total number of times throughout a 24 hour period patients indicate they will take medicine.

**Quality of Life.** We will use Patient Reported Outcomes Measurement Information System (PROMIS) Physical Function, Anxiety, Depression and Global Health subscales.

**Clinical Outcomes.** will be collected via EHR by site. Transplant-specific outcomes include: 1) change in estimated glomerular filtration rate (eGFR; ml/mn) over 24 months, 2) *Re-hospitalization*: Acute care hospitalizations 3) *Acute Rejection*: proven biopsy meeting organ-specific Banff criteria; 4) *Toxicity*: related to CNI medications (hypertension; neuro-toxic events); 5) *Infection*: CMV, BKV, bacterial infections assessed by laboratory tests and/or biopsies. *Blood pressure* (continuous SBP; control (y/n): SBP<140 & DBP<90) and *glycemic control (HbA1c)* will also be examined in those with hypertension and diabetes.

[figure not shown]

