### 9.11 Study Arms

Participants will be randomly assigned to either the TAKE IT strategy, as described in section 9.10 or usual care. Usual care refers to the normal standard clinical practices in place at either site, immediately post-transplant to the 5 years following. Northwestern and Mayo follow similar protocols for follow-up. KT recipients at both sites have lab values taken 3 times/weekly for the first 8-10 weeks post-transplant, shifting to weekly lab values for the next 3-4 months after, then monthly labs after. Both sites follow a similar tapering of weekly, to monthly to annual visits to the transplant nephrologist over the first 3 years. Protocol biopsies at both sites are taken between 3-6 months post-transplantation, at 12 then 24 months. All sites have a transplant nurse coordinator who has primary oversight of post-transplant care, full-time pharmacists and a clinical social worker. At Northwestern, the pharmacist has a standard visit with patients to review their prescribed regimen at discharge from the hospital. Social work and pharmacist visits are referrals as needed (PRN). At Mayo, both the pharmacist and social worker engage with patients only upon referral. Neither site has an active portal that engages KT recipients for any self-care support service.

**9.12 Data Sources.** Data sources for this study will include two in-person interviews and four phone interviews with participants, and Electronic Health Record chart review.

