### Aim 2.

Generalized linear mixed models (GLMMs) will be used to examine intervention effects over the course of the study. Link functions will be included as described above for the GLM models. Adherence concerns may differ in the two cohorts, thus separate models will be employed for each cohort (de novo, established). Treatment group will be the independent variable of primary interest, modeled as a fixed effect with the usual care group specified as reference group. We will also include fixed effects for site (NU, Mayo), time since transplant (in months), and potential confounding covariates noted in bivariate analyses. Random participant effects for each participant will be included to account for repeated measurements nested within each participant (assuming a compound symmetry, although we will fit autoregressive structures as well, comparing fit using AIC and BIC criterion). Outcomes recorded at each interview will be analyzed by visit whereas adherence measured by tacrolimus levels, along with blood pressure control will be analyzed in 6-month intervals as described above. A time-since-transplant-by-arm interaction term will be included to examine if outcome trajectories/slopes over time differ by study arm. Since prescription knowledge and adherence will be assessed for each medication, 2-level GLMM will be used for these outcomes with medications nested in participants. For  $\Delta$  eGFR and re-hospitalization outcomes, GLM models will be used since outcomes over 2 years are summarized in a single measurement. In the de novo cohort, change in eGFR from transplant to 2 years post-transplant and # hospitalizations (any hospitalization, if rare) within 2 years post-transplant will be modeled. For the established cohort, the time period for the both measures will span from transplant to 2-year study visit. It is possible those who do not complete the 2-year visit will differ in important characteristics (e.g. cognition, comorbidity), which could bias results. We will use collected data at prior interviews to understand the extent that individuals who complete follow-up differ from those who do not. If differences are found, pattern-mixture models will be employed by classifying participants' drop-out type or pattern (e.g. completed, refused, lost to follow up, death). This variable will then be added to mixed effects models to account for differences.

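### Change in eGFR is reduced to one start-to-end number per patient, outside the mixed models used elsewhere in Aim 2, which keeps avoidable noise and leaves out patients without a 2-year value

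*Combined protocol and SAP*

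**What the plan says.** Section 11.1, Aim 2, sets a general method: "Generalized linear mixed models (GLMMs) will be used to examine intervention effects over the course of the study", with random participant effects and a separate model for each cohort. Change in eGFR and re-hospitalization are then excepted: "GLM models will be used since outcomes over 2 years are summarized in a single measurement".

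The eGFR intervals are given by cohort. For new recipients: "In the de novo cohort, change in eGFR from transplant to 2 years post-transplant". For the others: "For the established cohort, the time period for the both measures will span from transplant to 2-year study visit". Section 8.4 words the outcome as "change in estimated glomerular filtration rate (eGFR; ml/mn) over 24 months" and takes it from the EHR. None of these places says which readings define the start and end values, or whether any are averaged.

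On routine labs, section 9.11 describes three draws a week at first, "shifting to weekly lab values for the next 3-4 months after, then monthly labs after". It does not name the analytes. Section 8.4 expects tacrolimus levels at a lower rate later on: "and 6-8 levels per year after the second year".

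Aim 1 lists change in eGFR as secondary, and its GLM adjusts for the baseline value of the outcome. Table 5 gives minimum detectable differences in change in eGFR of 2.9 (Total), 3.8 (de novo) and 4.6 (established), with a footnote that they refer to 2 years. The n of 610 behind the table rests on 1-year retention.

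**The concern.** The stated reason for leaving the mixed model is that the outcome is already a single number, but making it a single number is the choice in question. Re-hospitalization over a period is naturally one count. eGFR is a laboratory value that is probably recorded many times per patient.

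Three things follow. A difference between two readings contains the reading-to-reading noise twice. A patient without a 2-year value has no change score and drops out of the GLM. And the plan's answer to informative dropout, a dropout-pattern variable added to the mixed models, does not reach this outcome as written.

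Precision matters here because the detectable differences are large against the expected course. In de novo patients, 3.8 exceeds the whole expected usual-care decline of 3.0. In established patients, it is 4.6/8.0 = 58% of it.

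**Working it through.** **Inputs.** From Table 5: de novo 135 per arm, SD of change 11.0; established 170 per arm, SD 15.0; Total 305 per arm, SD 9.0. From the power paragraph: 5% type I error (two-sided assumed, since sidedness is not stated) and 80% power, so the multiplier is 1.960 + 0.842 = 2.802. The noise SD per reading, s, is not in the documents; 2, 4 and 6 ml/min are assumed. Aim 2 models the cohorts separately, so the cohort rows are the ones that apply.

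**Step 1: the plan's own figures.** Detectable difference = 2.802 × SD × √(2/n per arm).

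- De novo: 2.802 × 11.0 × √(2/135) = 3.75 (stated 3.8). Reproduces.
- Established: 2.802 × 15.0 × √(2/170) = 4.56 (stated 4.6). Reproduces.
- Total: 2.802 × 9.0 × √(2/305) = 2.04 (stated 2.9). Does not reproduce.

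A difference of 2.9 needs an SD of about 12.8. The printed 9.0 lies below both cohort SDs. Pooling the cohort SDs gives √[(270 × 121 + 340 × 225)/610] = 13.4, hence 3.03; adding the difference between cohort means gives 13.6, hence 3.09. The quality-of-life and blood-pressure rows reproduce with the same formula, so among the rows for means the fault is confined to this cell.

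**Step 2: averaging three readings at each end.** With independent noise, a change between single readings contains noise variance 2s². Means of three leave 2s²/3. The new variance is therefore SD² − (4/3)s². Power is at the stated 3.8 and 4.6.

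| Cohort | s | New SD | Detectable difference | Power |
|---|---|---|---|---|
| De novo | single readings | 11.0 | 3.75 | 0.81 |
| | 2 | √(121 − 5.3) = 10.75 | 3.67 | 0.83 |
| | 4 | √(121 − 21.3) = 9.98 | 3.40 | 0.88 |
| | 6 | √(121 − 48) = 8.54 | 2.91 | 0.96 |
| Established | single readings | 15.0 | 4.56 | 0.81 |
| | 2 | √(225 − 5.3) = 14.82 | 4.50 | 0.82 |
| | 4 | √(225 − 21.3) = 14.27 | 4.34 | 0.84 |
| | 6 | √(225 − 48) = 13.30 | 4.04 | 0.89 |

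Table 5 itself bounds s. Noise cannot exceed the whole de novo variance, so 2s² < 121 and s < 7.8; a value of 8 would give 128 and is impossible under this model. At s = 6, noise is already 72/121 = 60% of that variance, so this is a generous upper end.

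**Step 3: if values are sparse.** Six to eight draws a year is three to four per six months, just enough for a three-reading window mean if eGFR comes from the same draws. With only one value every six months, a straight-line fit through five values carries noise variance 576/(144 + 36 + 0 + 36 + 144) = 1.6s² instead of 2s². Power then rises from 0.81 to 0.82, 0.83 or 0.86 (de novo) and to 0.81, 0.82 or 0.83 (established): at most about 5 points.

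**Step 4: missing 2-year values.** The retention of 85–90% behind n = 610 is for 1 year, while the eGFR row covers 2 years. The documents give no 2-year figure, so the number lost from the GLM cannot be computed.

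**The case against.** The strongest reply is that this is a matter of efficiency in a secondary outcome. The estimate is not biased by reading noise, and the cohort rows use the SD of the change itself, so they keep about 80% power for their stated differences. That stands. A reader might infer that the eGFR comparison is underpowered against its own plan, or that eGFR is the main transplant outcome. The documents support neither: H3 lists it beside quality of life and re-hospitalization, and Aim 1 calls it secondary.

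Second, the plan never says that only one reading is used at each end. Means of several readings would still be one number per patient and would fit the text. That also stands: the noise part of the point concerns a definition left open as much as a wrong choice. The loss of patients without a 2-year value does not depend on it.

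Third, frequent eGFR values are inferred. Section 9.11 says only labs, and section 8.4 gives a lower tacrolimus frequency after year two. The inference is reasonable but needs confirming at both sites.

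Fourth, the GLM's baseline adjustment may already remove part of the start-value noise, and three readings taken within a week soon after transplant are unlikely to be independent. Both would make the gain smaller than shown.

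Fifth, a model on every routine value has its own hazards: sicker patients are sampled more often, the intervention may alter lab contact in one arm, and eGFR need not be linear soon after transplant. This is a good argument against a simple slope on all values, and it is why the change below uses fixed windows.

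**Conclusion.** The point holds as a worthwhile, inexpensive improvement to a secondary analysis. The plan leaves eGFR out of a method that it already uses, for a circular reason. The direction of the precision gain is sure if any independent reading noise exists; its size is not known. Over assumed noise of 2 to 6 ml/min, the detectable difference falls by 0.08 to 0.84 ml/min in de novo patients (3.75 to between 3.67 and 2.91) and by 0.06 to 0.52 in established patients (4.56 to between 4.50 and 4.04). The loss of patients without a 2-year value, and the gap in the dropout remedy, follow from the text and need no noise assumption.

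It would be tempting to express the gain on the pooled sample against 2.9. That does not match the cohort-specific models and uses a table row that fails its own arithmetic. The Total row is a separate error to correct.

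**What to change.** **Main change.** Within each cohort, fit a linear mixed model to outpatient eGFR in fixed windows after randomisation, for example 6-monthly. Use one value or, preferably, the window mean per patient and window, and exclude readings taken during acute illness, as section 8.4 already does for tacrolimus. Take the mean of several pre-randomisation readings as baseline covariate, treat time as categorical, and estimate the arm difference at 24 months. With complete data, the precision comes from the window and baseline means; the intermediate windows serve mainly to retain patients without a 24-month value. Extend the dropout-pattern analysis to this model.

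**Sensitivity analysis.** Keep the planned change from transplant. The new estimate starts at randomisation, whereas the planned one includes time before it: up to 24 months in established patients, for a total interval of up to 24 + 24 = 48 months. Section 8.4's 24-month wording should be aligned with whichever interval is used.

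**Minimum version.** Keep the GLM, but define the start and end values as means of several outpatient readings in stated windows.

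**Also.** Confirm that eGFR is part of the routine draws, reconcile the lab frequencies in sections 8.4 and 9.11 after year two, and correct the SD, the detectable difference or both in the Total eGFR row of Table 5.

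**Cost.** A wider EHR pull of a value already extracted, modest extra analysis, and a primary eGFR estimand that starts at randomisation.

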## **7.0 Study Timelines:**

**7.1** We anticipate the entire study will take 5 years to complete. See study timeline below.

**7.2** An individual patient will be involved in the study for a total of up to 24 months. They will complete a screener enrollment interview via phone, a baseline interview in-person and a 6-week and 6-month interview via phone. A 12-month and an 18 month interview will be conducted either in-person or over the phone\*, with the remaining 24-month interview administered via phone. \*If the 12-month interview cannot be done in person due to the timing of clinic visits, it will be done over the phone and we will attempt to do the 18 month interview in person.

**7.3** We anticipate that patient enrollment will actively take place over 2.5 years. The date by which we expect to complete primary analyses is March 2021.

Table 2. Study Timeline TASKS	Year 1				Year 2				Year 3				Year 4				Year 5			
	1	2	3	4	1	2	3	4	1	2	3	4	1	2	3	4	1	2	3	4
PREPARATION PHASE:																				
Organize research team, convene DSMB	■																			
Protocol development at sites, train research team	■																			
Purchase laptops and software	■																			
Pilot test and refine assessment tools	■																			
Develop web portal, activate EHR tools & de-bug	■	■																		
Prepare SMS text service	■	■																		
Program database and laptop interface	■																			
Pilot TAKE IT	■																			
IMPLEMENTATION PHASE:																				
Recruit, consent, and randomize participants		■	■	■	■	■	■	■	■	■	■	■	■	■	■	■	■	■	■	■
Conduct baseline interviews		■	■	■	■	■	■	■	■	■	■	■	■	■	■	■	■	■	■	■
Implement Intervention		■	■	■	■	■	■	■	■	■	■	■	■	■	■	■	■	■	■	■
Conduct follow up interviews			■	■	■	■	■	■	■	■	■	■	■	■	■	■	■	■	■	■
Seek process feedback from clinic staff							■				■				■				■	
Extract EHR, pharmacy data							■				■				■				■	
EVALUATION PHASE:																				
Clean & analyze data					■	■	■	■	■	■	■	■	■	■	■	■	■	■	■	■
Summarize and interpret findings																		■	■	■
Provide feedback to sites																		■	■	■
Submit manuscripts for publication					■			■			■				■			■	■	■
Present findings at national venues					■			■			■				■			■	■	■

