*Power Calculation.* The sample size calculation was based on the availability of 700 transplant patients estimated by the number of transplants conducted in 2012-2014 across the two sites. With the sample size set at 610 accounting for 85-90% retention at 1 year, we present the minimum differences we will be able to detect between the intervention and usual care arms for each outcome of interest. For the main outcome of medication adherence, we estimate 45% of the sample to be non-adherent using the composite score described above taking estimates for each individual measure into account. We will have sufficient power ( $\geq 80\%$ ) to detect differences of 11% in the entire sample assuming a 5% Type I error rate. Should TAKE IT be associated with potential confounders, calculations show that an R-squared of 0.2 between predictors (a conservatively high estimate under randomization), we would still maintain 70% power to detect the 11% difference. Although adjusting for confounders would decrease variability in adherence, and increase power. Detectable differences for individual adherence measures along with estimates and effect sizes for other outcomes of interest are listed in Table 5.

Table 5. Detectable Differences in Health Outcomes between Study Arms at 1 Year

Outcome	Total (n=610) 305/arm		De Novo (n=270) 135/arm		Established (n=340) 170/arm	
	Usual Care Estimate	Minimum Difference	Usual Care Estimate	Minimum Difference	Usual Care Estimate	Minimum Difference
Primary Outcomes						
Rx Knowledge, %	50	11.3	60	15.9	45	15.1
Rx Non-adherence, %	45	11.0	35	15.2	50	15.0
Self-report, %	35	10.3	29	14.1	44	14.6
Objective (pill count), %	45	11.1	35	11.3	50	15.0
Claims (PDC), %	30	9.8	23	12.7	38	14.0
Biologic (SD Tacrolimus), %	40	10.8	30	14.3	45	14.7
Secondary Outcomes						
Quality of life, mean(SD)	46.2 (9.0)	2.0	45.8 (7.2)	2.5	49.5 (9.0)	2.7
Clinical outcomes						
$\Delta$ eGFR, mean(SD)*	-5.8 (9.0)	2.9	-3.0 (11.0)	3.8	-8.0 (15.0)	4.6
Re-hospitalizations, %	40	10.8	32	14.6	47	14.8
Systolic BP, mean(SD)**	136.7 (8.3)	2.2	138.3 (12.9)	5.1	135.0 (7.9)	2.8

\* $\Delta$  eGFR estimates over 2 years

[figure not shown]
\*\*estimate 75% of cohort has hypertension (Total: n=458, 229/arm; De Novo: n=202, 101/arm; Established: n=256, 128/arm)

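### In the de novo cohort the 2-year eGFR-change and hospitalisation outcomes close before the 24-month study visit, so the last part of randomised follow-up, about 5-6% at the documented entry time, goes unused

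*Combined protocol and SAP*

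**What the plan says.** The Aim 2 text in section 11.1 summarises change in eGFR and re-hospitalisation as one measurement per patient and sets a different window for each cohort.

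- De novo, eGFR: "In the de novo cohort, change in eGFR from transplant to 2 years post-transplant".
- De novo, hospitalisation: "hospitalizations (any hospitalization, if rare) within 2 years post-transplant will be modeled".
- Established, both outcomes: "the time period for the both measures will span from transplant to 2-year study visit".

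Other places bear on the end date:

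- Section 3.2 admits patients from 5 weeks to 24 months after transplant.
- Section 7.2 states: "An individual patient will be involved in the study for a total of up to 24 months". Section 9.1 says patients are followed for 2 years after recruitment.
- Sections 5.2 and 22.2 identify de novo patients at Mayo as 6 weeks post-transplant. No upper limit for the de novo cohort is given anywhere.
- Section 8.4 lists "change in estimated glomerular filtration rate (eGFR; ml/mn) over 24 months" without saying when the 24 months begin. It gives no window for re-hospitalisation.
- The Exploratory Analyses paragraph counts rejection, toxicity and infection over the whole study.
- Table 5 is titled "Detectable Differences in Health Outcomes between Study Arms at 1 Year", but its change-in-eGFR row carries the footnote "eGFR estimates over 2 years".

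**The concern.** A de novo patient enrolled e months after transplant is followed to 24 + e months after transplant, but these two outcomes stop at 24. The last e months of randomised follow-up are planned for collection and then not used. Aim 2 asks whether effects persist over 2 years, so the months dropped are the latest ones. The established cohort and the exploratory outcomes keep theirs. A rejection late in study follow-up would be counted, while a hospitalisation for it in a de novo patient would not.

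What is at stake is some power for two secondary outcomes in one cohort, and two outcomes described as 2-year results whose windows differ between cohorts. Table 5 has a related gap: a 2-year eGFR outcome is sized on the number retained at 1 year.

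**Working it through.** **Inputs.** From the documents: 135 per arm in the de novo cohort, usual-care re-hospitalisation 32%, detectable difference 14.6 points, 80% power and 5% type I error (Power Calculation and Table 5); entry from 5 weeks (section 3.2) or 6 weeks (sections 5.2 and 22.2); 2 years of follow-up (sections 7.2 and 9.1). Assumed: two-sided testing; enrolment, baseline interview and randomisation on the same date; and, for power, the 32% taken as a 24-month risk, because Table 5 does not make its period clear.

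**Reproducing the plan's figures.** A two-proportion test with pooled variance and no continuity correction, for a reduction from 32% with 135 per arm, gives a detectable difference of 14.64 points against 14.6 stated. Power at 14.6 points (32% against 17.4%) is 79.8%. For de novo eGFR, 2.80 × 11.0 × √(2/135) = 3.75 against 3.8 stated.

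**Follow-up unused.** Months unused = (24 + e) − 24 = e.

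| Entry after transplant | Months unused | Share of 24 |
|---|---|---|
| 5 weeks (documented) | 1.15 | 4.8% |
| 6 weeks (documented, Mayo) | 1.38 | 5.7% |
| 3 months (assumed) | 3 | 12.5% |
| 6 months (assumed) | 6 | 25% |
| 12 months (assumed) | 12 | 50% |

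**Illustrative power, any hospitalisation.** Assume a constant hazard and no effect before randomisation. Usual care: −ln(0.68)/24 = 0.01607 per month. Intervention: −ln(0.826)/24 = 0.00797 per month. The plan counts from transplant, so the e months before randomisation carry the usual-care hazard in both arms.

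- Planned window (transplant to 2 years post-transplant): usual care 32%; intervention 1 − exp(−0.01607e − 0.00797(24 − e)).
- Only the end moved to the 24-month visit: usual care 1 − exp(−0.01607(24 + e)); intervention 1 − exp(−0.01607e − 0.00797 × 24).
- Baseline to the 24-month visit: 32% against 17.4%.

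| Entry | Planned window | End moved only | Baseline to 24-month visit |
|---|---|---|---|
| 6 weeks | 32.0% v 18.3%: power 73.8% | 33.5% v 19.2%: power 76.2% | 79.8% |
| 6 months (assumed) | 32.0% v 21.3%: power 51.0% | 38.2% v 25.0%: power 65.0% | 79.8% |

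Moving the end recovers part of the loss. The rest comes from the start date, because pre-randomisation time dilutes the contrast. The start date matters more for the established cohort: a patient enrolled at 24 months has a 48-month window, half of it before randomisation.

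**Table 5, eGFR.** No 2-year retention is stated. If the second year repeats the first-year loss (90% retained de novo, 85% established; an assumption), the numbers per arm become 135 × 0.90 = 121.5 and 170 × 0.85 = 144.5. The detectable differences are then:

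- De novo: 2.80 × 11 × √(2/121.5) = 3.95, against 3.75.
- Established: 2.80 × 15 × √(2/144.5) = 4.94, against 4.56.

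**The case against.** The strongest reply is that the loss is small and that the end date alone is not the main weakness. Both parts stand. On the only de novo entry time documented, about 6% of follow-up goes unused; every larger figure needs an entry boundary that the plan does not state. Moving only the end would leave pre-randomisation time in the window. It would also turn a fixed 24-month de novo count into one of varying length, so the start has to be corrected as well.

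Four stronger readings are tempting, and the documents do not support them.

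- **Section 8.4 contradicts Aim 2.** Its 24 months have no stated origin and cover eGFR only. Transplant to 2 years post-transplant is also 24 months, so the text is ambiguous, not contradictory.
- **The differing windows spoil a combined analysis.** Aim 2 specifies separate models by cohort, and no pooled 2-year analysis of these outcomes is described.
- **Late effects are lost to Aim 2.** Its mixed models use all visits or 6-month intervals for the repeated outcomes. Only these two single-measurement outcomes are cut short.
- **Data already in hand are thrown away.** The documents are a plan; they schedule the EHR extraction and do not report it as done.

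On Table 5, the footnote does disclose the 2-year horizon. Because eGFR comes from the EHR, interview retention may also not be the right denominator. The sizing point is therefore minor.

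**Conclusion.** The point holds as a limited one. For change in eGFR and hospitalisation, the de novo window closes before the 24-month visit by exactly the transplant-to-enrolment interval. That is 1.15 to 1.38 of 24 months at 5-6 week entry, and more only if later entrants count as de novo. In the illustration at 6-week entry, power is about 74% as planned, 76% with the end moved and 80% with baseline as the start. At an assumed 6-month entry the figures are 51%, 65% and 80%. These rest on a constant hazard, 32% against 17.4% over 24 months, 135 per arm and no effect before randomisation.

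The eGFR detectable differences become about 4.0 and 4.9 instead of 3.8 and 4.6 only under the assumed second-year loss. The change is worth making because it costs little. The primary outcome, adherence at 1 year, is unaffected.

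**What to change.** - **Aim 2 text, section 11.1:** define both outcomes, in both cohorts, from the baseline interview/randomisation to the 24-month study visit, with baseline eGFR as the reference for change. If any count window of varying length is kept, include a log-exposure offset.
- **Section 8.4:** state the same origin for the 24 months, and give re-hospitalisation a window.
- **De novo cohort:** state its upper entry limit, and keep the 2-years-post-transplant figures as descriptive results.
- **Table 5:** label the eGFR row as a 2-year outcome outside the 1-year heading, and base it on an explicit 2-year analysable number.

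The cost is mainly wording. Clinical outcomes come from the EHR and follow-up to 24 months is already planned, so little or no new data collection should be needed. The price is losing the fixed post-transplant horizon as the modelled outcome for de novo patients, and a slightly less favourable eGFR detectable difference.
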